1.6 Risk analysis

This study is considered to be a non-significant risk study based on United States Food and Drug administration (FDA) and International Standards Organization (ISO) guidelines due to the daily wear nature of the study. With the potential benefit of this study, the work is considered to be ethically justifiable. Ethical approval will be sought from the University of Manchester Senate Committee on the Ethics of Research on Human Beings (hereafter referred to as Manchester UREC). The work where practical will be conducted in

accordance with the ICH Good Clinical Practice Guidelines and the international standard BS EN ISO 14155:2011 'Clinical investigation of medical devices for human subjects'.

Section 2. Resources

2.1 Subject selection

In this work, up to 35 subjects will be consented with the aim of 15 subjects completing the study in each group.

2.1.1 Subject withdrawal and replacement

This study includes two clinical visits. Once the study consent form is signed, the subject is considered to be enrolled on the study. Subjects who have signed the consent form, but who have not completed the dispensing visit will usually be replaced. All subject data will be included in the final analyses unless there are strong grounds for exclusion; such grounds will be detailed in the final report.

2.1.2 Subject recruitment

Subjects will be recruited by one or more of following means:

1. Posting study details on The University of Manchester's 'Research Volunteers' website.
2. Correspondence to existing subjects on the Eurolens Research database of subjects.
3. Advertising through a variety of media via a format separately approved by Manchester UREC.

2.1.3 Inclusion criteria

Subjects will only be eligible for the study if:

1. They are aged between 18 and 40 years.
2. They understand their rights as a research subject and are willing and able to sign a Statement of Informed Consent.
3. They are willing and able to follow the protocol.
4. They are a 'neophyte' (i.e. someone who has not worn contact lenses previously, with the exception for the purposes of a trial fitting).
5. They have a contact lens spherical prescription between +8.00D and -10.00D (inclusive) based on the ocular refraction.
6. They have a cylindrical correction of -0.75DC or less in each eye based on the ocular refraction.
7. They own and habitually wear single vision spectacles.
8. They are willing to be fitted with contact lenses and understand they may be randomised to either group.

9. They are willing to wear the contact lenses (if relevant) or spectacles for at least 8 hours per day, 5 days per week.
10. They are able to wear the supplied surgical masks for the majority of time that they need to wear PFM and will wear the PFM for at least one hour a day for at least four days per week.
11. They can attain at least 0.20 logMAR distance high contrast visual acuity in each eye with the study lenses (if relevant) or spectacles.
12. They agree to not participate in other clinical research while enrolled on this study.

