Clinical investigation plan

C20-688 (EX-MKTG-120)

Using personal face masks with spectacles
versus contact lenses

A clinical evaluation for CooperVision Inc.

Study Leader
[name]

Principal Investigator
[name]

September 2020

Contents

Section 1. Overview	5
1.1 Background	5
1.2 Personnel	5
1.3 Study objectives	5
1.4 Study design	5
1.5 Statistical considerations	6
1.6 Risk analysis	6
Section 2. Resources	8
2.1 Subject selection	8
2.2 Subject discontinuation	9
2.3 Safety parameters, adverse events and concurrent illnesses	10
2.4 Study termination	10
2.5 Protocol deviations	10
2.6 Study resources	11
2.7 Study control	12
2.8 Documentation	12
2.9 Data collection and analysis	12
2.10 Study completion	12
2.11 Confidentiality	12
2.12 Study monitoring	12
2.13 Clinical trial registration	13
Section 3. Subject management	14
3.1 Visit scheduling	14
3.2 Visit conduct	14
3.3 Monitoring subject compliance	20
3.4 Missing, unused and spurious data	20
Section 4. Study co-ordination	21
4.1 Document processing	21
4.2 Disclosure	21
4.3 Personnel	21

Study summary

The aim of this study is to explore (a) satisfaction with vision correction and (b) ease of use of personal face masks (PFM) in a group of spectacle wearers and a group of newly-fitted contact lens wearers. This will be a two-arm, parallel-group, randomised study. Up to 35 single vision spectacle wearers will be recruited to participate in the study. Subjects will be randomised to either continue to wear their spectacles or to be fitted with the study daily disposable (DD) contact lens (clariti 1 day, CooperVision Inc.), for a period of two weeks.

[REDACTED]

[REDACTED]

A study summary is shown in Table 1.

V st	Procedures
Inta v st	
Information and consent forms signed
 
Medical and ocular histories
 
[REDACTED] visual acuity
 
Subjective scores and questionnaires
 
[REDACTED]
 
Confirmation of eligibility
 
Randomisation to treatment type
 
Vision, subjective scores, [REDACTED] (contact lens group only)
 
Contact lens application/removal/education session (contact lens group only)
 
[REDACTED]

2 week v st	
Medical and ocular histories
 
Subjective scores and questionnaires
 
Visual acuity
 
[REDACTED]
 
Study exit and payment issued

Table 1: Study summary.

Section 1. Overview

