2.2 Subject discontinuation

In general, subjects should be discontinued at any time, if it is in their best interests, as judged by the investigator. Reasons for this may include clinical signs of grade 3 or more, lack of motivation, discomfort, repeated refusal to follow instructions or the use of non-

study products such as solutions or lenses. Subjects will be discontinued if a serious adverse event occurs. Subjects who fail to satisfy all the inclusion and exclusion criteria will be discontinued and replaced. Subjects may choose to leave the study at their own request. All discontinuations will be carefully recorded.

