12. Slit lamp biomicroscopy will be carried out for the signs outlined in Table 4 and in accordance with the current Eurolens Research Standard Operating Procedure 'Examination of the anterior segment using slit lamp biomicroscopy'. Grades will be scored to the nearest 0.1 unit in the best judgement of the investigator using Efron Grading Scales. Corneal staining will be graded for five regions (central, superior, temporal, inferior and nasal) as well as an 'overall' grade. The predominant type of corneal staining present will also be recorded.

Classification	Primary signs	Secondary signs
Signs	Conjunctival redness Limbal redness Corneal neovascularisation Epithelial microcysts Corneal oedema Corneal staining Location of staining Conjunctival staining Papillary conjunctivitis	Bephrats Meibomian gland dysfunction Mucin bands
Score	Efron Grading Scores (scored to nearest 0.1)	Efron Grading Scores (scored to nearest 0.1) (except mucin bands, where the number is recorded)

[figure not shown]
Table 4: Biomicroscopic signs. Staining assessed with sodium fluorescein.

The presence of any adverse events will be recorded [REDACTED]

13. The investigator will confirm that the subject satisfies all the inclusion and exclusion criteria. Subjects who fail to meet all the criteria at this time will usually be discontinued and replaced.

14. The subject will be randomised to one of the two treatment groups. For subjects assigned to the spectacle group, proceed to step 22.

15. For those assigned to the contact lens group, the study lenses will be fitted and allowed to settle for five minutes or until tearing stops (whichever is the longer).
16. Monocular logMAR visual acuity (high contrast) will be recorded before performing an over-refraction, and then monocular logMAR visual acuity (high and low contrast) will be carried out with the over-refraction in place, and in accordance with the current Eurolens Research Standard Operating Procedure 'The setup, measurement of visual acuity and procedures for carrying out an over refraction using Eurolens computerised logMAR VA chart'.

21. Subjects will be trained on contact lens application, removal and best practice immediately at the end of the visit or at a later date if required. More than one visit is possible for this 'teaching' session if there are problems with handling. Subjects will be dispensed with contact lenses only once the investigator is satisfied with their ability to successfully apply and remove lenses.

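### The study-lens part of inclusion criterion 11 and the handling condition for dispensing act after randomisation, in the lens arm only, and the visible plan does not provide for two-week scores from subjects who fail them

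*Combined protocol and SAP*

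**What the plan says.** Criterion 11 in section 2.1.3 is "They can attain at least 0.20 logMAR distance high contrast visual acuity in each eye with the study lenses (if relevant) or spectacles". It has two limbs: study lenses where they apply, and spectacles.

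Section 3.2.2 fixes the order of events:

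- Step 6: refraction and acuity in every subject. The text does not say whether this acuity is taken with spectacles or with the refraction.
- Step 13: "The investigator will confirm that the subject satisfies all the inclusion and exclusion criteria", followed by "Subjects who fail to meet all the criteria at this time will usually be discontinued and replaced".
- Step 14: randomisation, then "For subjects assigned to the spectacle group, proceed to step 22".
- Step 15: study lenses fitted, lens arm only.
- Step 16: "Monocular logMAR visual acuity (high contrast) will be recorded before performing an over-refraction", the first acuity with study lenses.
- Step 21: "Subjects will be dispensed with contact lenses only once the investigator is satisfied with their ability to successfully apply and remove lenses".

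Table 1 of the study summary gives the same order: eligibility, randomisation, then items such as "Contact lens application/removal/education session (contact lens group only".

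On the consequence of failing a criterion, section 2.2 states: "Subjects who fail to satisfy all the inclusion and exclusion criteria will be discontinued and replaced". Section 2.1.1 says that consented subjects who have not completed the dispensing visit are usually replaced, and that all subject data are analysed unless there are strong grounds for exclusion. In Table 3 of section 3.1 the two-week target is counted from dispensing, while the allowable range is 10 to 20 days from the initial visit. The principal hypothesis in section 1.5 is that the two groups have the same subjective scores.

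**The concern.** Step 13 asks the investigator to confirm all criteria, yet the study-lens limb of criterion 11 cannot be known until step 16. By then the subject has been allocated, and only the lens arm is tested. Read literally, section 2.2 then discontinues a randomised lens-arm subject on a result that no spectacle subject can have. A subject who does not pass the handling condition at step 21 is not dispensed and is usually replaced.

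Randomisation is the bias control that section 2.7 names. A filter that acts after allocation in one arm, with no outcome collected from those filtered out, can leave groups that are no longer the groups randomised. With an aim of 15 completers per group, one or two subjects matter: 1 of 16 is 6% of the lens arm and 2 of 17 is 12%.

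**Working it through.** **Is there a figure to reproduce?** No. The visible text gives no failure rate, dropout rate, SD, alpha or power. It gives up to 35 consented and an aim of 15 completers per group (section 2.1), so the spare is 35 − 2 × 15 = 5. Subjects count as enrolled at consent, so those 5 must cover screening failures and losses in both arms.

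**Is there a route to two-week scores for a randomised lens-arm subject who fails?**

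- *Acuity at step 16.* Section 2.2 discontinues and replaces. Step 13 has a version limited to that moment and qualified by usually; section 2.2 has neither limit. The two do not agree.
- *Handling at step 21.* This is not an inclusion criterion, so section 2.2 does not reach it through its criteria rule. Section 2.1.1 applies: usually replaced. It says nothing on follow-up.
- *Section 3.1, Table 3.* An undispensed subject has no target date, although the allowable range can still be computed.
- *Section 3.2.3.* Lens-arm subjects who arrive without lenses in place for two hours are usually rescheduled, which does not help someone who has no lenses.
- *Section 3.1.2.* Non-attenders are encouraged to return. This covers missed visits, not subjects discontinued or never dispensed.
- *Sections 2.1.1 and 3.4.* Including all data, using partial datasets and reporting numbers analysed keep what was collected. They do not create a two-week score.

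**How large could the effect be?** Illustration only. Assumptions: the k lens subjects with the lowest lens tolerance are lost and replaced up to 15 completers; tolerance and score correlate at r; scores are normal with SD 1; there is no true difference; the test is a two-sided 5% t-test.

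Shift in the lens mean = r × φ(z_q) / (1 − q), where q = k/(15 + k) and z_q is the normal quantile of q.

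- k = 1: q = 0.0625, φ = 0.123, 0.123/0.9375 = 0.131. With r = 0.3 to 0.7 the shift is 0.04 to 0.09 SD.
- k = 2: q = 0.118, φ = 0.197, 0.197/0.882 = 0.224. Shift 0.07 to 0.16 SD.
- k = 3: q = 0.167, φ = 0.250, 0.250/0.833 = 0.300. Shift 0.09 to 0.21 SD.
- r = 0: shift 0 for any k.

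Simulated chance of a significant result favouring lenses, against a nominal 2.5%: about 3% (k = 1, r = 0.3), 5% (k = 2, r = 0.5) and 6% (k = 3, r = 0.5).

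Without replacement, from a fixed 15, two losses give 0.075 to 0.174 SD, slightly more than with replacement. The missing scores are therefore the mechanism, not the replacement.

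Similar losses in the other arm cancel the shift: at r = 0.5, two lens losses and one spectacle loss leave 0.05 SD, and two and two leave 0.

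**How likely is any loss?** The documents give no rate. At an assumed 5% to 20% combined failure rate, the chance of at least one loss among 17 is 1 − 0.95^17 = 58% to 1 − 0.80^17 = 98%.

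**What would comparing all randomised subjects cost?** Suppose non-wearers score like spectacle wearers. The lens-arm difference is then diluted to 15/16 = 94%, 15/17 = 88% or 15/18 = 83% of the wearers' difference. The mixture also widens the lens-arm SD. At a true wearer difference of 1.06 SD, which gives 80% power with 15 against 15, simulation gives power of about 75%, 70% and 66% with 1, 2 and 3 non-wearers.

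**The case against.** The strongest reply has five parts.

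*Criterion 11 has a workable reading.* At step 13 nobody has study lenses, so the spectacle limb can be judged in everyone, and the wording of step 13 fits that. This stands. A reader might infer that the whole criterion is unknowable before randomisation; only the study-lens limb is.

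*Acuity failure is improbable.* The cylinder limit is −0.75DC and the sphere range in criterion 5 matches the lens powers in Table 2. This stands too. Handling is the likelier route, since every subject is new to lenses and step 21 itself foresees handling problems. A reader might infer that the plan orders handling failures out of follow-up. It does not: section 2.1.1 only says they are usually replaced. The gap there is silence, not a rule.

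*The bias figures rest on an unsupported correlation.* An undispensed subject would probably give two-week scores in spectacles, and nothing in the documents links lens handling to those scores. If non-wearers score like spectacle wearers, as the power figures assume, then with no true difference r is 0 and so is the shift. The shifts and the power figures are therefore alternative scenarios, not joint predictions.

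*A rule may exist out of sight.* Steps 17 to 20 and section 1.5.1 cannot be seen, nor can parts of sections 1.5 and 3.2.3. A lens-acceptance rule or an analysis-set definition could be there. The point is limited to the visible text.

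*The study explores newly fitted wearers.* The study summary uses that phrase, which favours an analysis of wearers. But section 1.3 describes spectacle wearers who will be randomised to one correction or the other, which favours comparison by allocation. Both analyses can be given.

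What remains is the step order, the mismatch between step 13 and section 2.2, and the absence of any visible provision for the two-week scores.

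**Conclusion.** The point holds as a should-fix, with moderate confidence. The study-lens limb of criterion 11 and the handling condition both operate after allocation and in one arm only. Section 2.2 as written would discontinue a randomised subject on the first. Neither route has a visible path to two-week scores.

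The documents do not show that the comparison is biased, or biased towards lenses. The bias is nil if nobody fails, if failure is unrelated to the scores, or if matching losses occur among spectacle subjects. The range of 0.04 to 0.21 SD for one to three losses depends on the assumed correlation of 0.3 to 0.7 and should be quoted only with it. The case for change rests on structure: the order is fixed in the text, the arms are small, and scores never collected cannot be recovered in analysis.

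**What to change.** 1. Reconcile criterion 11, step 13 and section 2.2. State which acuity, taken with which correction, decides eligibility before randomisation. State also that a lens-arm acuity result obtained after randomisation does not remove the subject from the study data. Decisions on fitting, dispensing and stopping lens wear stay with the investigator.
2. State in sections 2.1.1 and 2.2 that a randomised subject stays in the analysis in the allocated group, even if an additional subject is recruited.
3. Seek the two-week scores and questionnaires from every randomised subject, including those never dispensed, within the existing Table 3 range. Confirm that the mask supply at step 22, which is headed for both groups, includes them.
4. In section 1.5, compare all randomised subjects by allocated group and give subjects wearing the allocated correction as a supporting analysis. Add to the section 3.4 reporting the number lost after randomisation, by arm and step.

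The cost is wording in a few sections and a handful of extra questionnaires, with no extra lens fitting. The main comparison loses some power to dilution: roughly 5 percentage points per non-wearer under the assumptions shown. The supporting analysis keeps the answer for newly fitted wearers.

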2.1.4 Exclusion criteria

Subjects will not be eligible to take part in the study if:

1. They have an ocular disorder which would normally contra-indicate contact lens wear.
3. They have a systemic disorder which would normally contra-indicate contact lens wear.
4. They are using any topical medication such as eye drops or ointment.
5. They have had cataract surgery.
6. They have had corneal refractive surgery.
7. They have any corneal distortion resulting from previous hard or rigid lens wear or have keratoconus.
8. They are pregnant or breastfeeding.
9. They have any ocular abnormality which would, in the opinion of the investigator, normally contraindicate contact lens wear.
10. They have any infectious disease which would, in the opinion of the investigator, contraindicate contact lens wear or pose a risk to study personnel; or they have any immunosuppressive disease (e.g. HIV), or a history of anaphylaxis or severe allergic reaction.
11. They require significant ocular/face personal protective equipment beyond a personal face mask.
12. They have taken part in any other contact lens or care solution clinical trial or research, within two weeks prior to starting this study.
13. They have spectacles which are not within $\pm 0.50\text{D}$ of their refractive error.

2.2 Subject discontinuation

In general, subjects should be discontinued at any time, if it is in their best interests, as judged by the investigator. Reasons for this may include clinical signs of grade 3 or more, lack of motivation, discomfort, repeated refusal to follow instructions or the use of non-

study products such as solutions or lenses. Subjects will be discontinued if a serious adverse event occurs. Subjects who fail to satisfy all the inclusion and exclusion criteria will be discontinued and replaced. Subjects may choose to leave the study at their own request. All discontinuations will be carefully recorded.

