3.1 Visit scheduling

Subjects will be required to attend two visits – an initial visit and one follow-up visit. Acceptable date ranges are shown in Table 3. Subjects in the contact lens group may need to attend for more than one ‘teach’ session.

Vst	Target	Allowable range
Initial vst	N/A	N/A
2 week Follow-up	14 days from dispensing 1	10-20 days from initial vst

Table 3: Visits and allowable ranges.

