3.1.2 Missed visits

Subjects not attending for a visit will be contacted and encouraged to return for assessment.

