3.2.3 Follow-up visit

*For the contact lens group, subjects should attend wearing the study lenses which should have been *in situ* for at least two hours. Subjects who attend without lenses *in situ* for at least two hours will usually be rescheduled. For the spectacle group, subjects should attend wearing their spectacles. Spectacles should have been worn for a minimum of two hours on the day of the visit.*

The following procedures will be performed:

1. Any medical or ocular issues since the last visit.
2. Spectacle or contact lens wearing times since the previous visit (hours per day, days per week and comfortable hours per day).
3. Spectacle or contact lens wearing time on study visit day.
4. Surgical mask wearing times since the previous visit (hours per day, days per week and comfortable hours per day).
5. [REDACTED]
6. Facemask usability questionnaire will be completed [REDACTED]
7. [REDACTED]
- [REDACTED]
- [REDACTED]
- [REDACTED]
- [REDACTED]

[REDACTED]

[REDACTED]

[REDACTED]

[REDACTED]

[REDACTED]

8. Questions about using the mask during day-to-day activities/tasks [REDACTED]

[REDACTED]

9. [REDACTED]

[REDACTED]

[REDACTED]

[REDACTED]

[REDACTED]

[REDACTED]

[REDACTED]

[REDACTED]

[REDACTED]

11. For spectacle wearers, monocular logMAR visual acuity (high contrast) will be recorded. Proceed to step 15.

12. For contact lens wearers, monocular logMAR visual acuity (high contrast) will be recorded before performing an over-refraction, and then monocular logMAR visual acuity (high and low contrast) will be carried out [REDACTED] as described in section 3.2.2.

13. [REDACTED]

[REDACTED]

[REDACTED]

[REDACTED]

15. The subject will be issued with their payment and discharged.

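### Lens-arm subjects can be replaced after randomisation for acuity or handling failure, and no exit scores are visible for discontinued subjects, so the two-week subjective comparison may be biased towards lenses

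*Combined protocol and SAP*

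**What the plan says.** Section 1.5 makes equality of subjective scores in the two groups the principal hypothesis. Table 1 lists subjective scores and questionnaires at the initial and two-week visits only, apart from subjective scores for the lens group after randomisation at the initial visit.

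Four sets of rules decide who supplies a two-week score:

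- **Replacement.** Section 2.1.1: "Subjects who have signed the consent form, but who have not completed the dispensing visit will usually be replaced". Section 2.2 adds that subjects who do not meet all entry criteria are discontinued and replaced.
- **Discontinuation.** Section 2.2: "subjects should be discontinued at any time, if it is in their best interests, as judged by the investigator". Reasons may include "lack of motivation, discomfort, repeated refusal to follow instructions". The wording is not specific to either arm.
- **Follow-up attendance.** Section 3.2.3: lens subjects who arrive without lenses in place "for at least two hours will usually be rescheduled". For the other arm it says "Spectacles should have been worn for a minimum of two hours on the day of the visit", with no stated consequence. Table 3 allows "10-20 days from initial" visit, and section 3.1.2 adds: "Subjects not attending for a visit will be contacted and encouraged to return for assessment".
- **Analysis.** Section 2.1.1 includes all subject data "unless there are strong grounds for exclusion". Section 3.4 admits partial datasets where appropriate and requires the number analysed to be reported.

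**The concern.** Randomisation protects the comparison only if the people scored at two weeks are the people randomised, or if those missing are missing for reasons unrelated to their scores. Two features of the plan threaten this.

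First, some lens-arm subjects can be replaced after allocation because the lenses did not work for them. A subject who cannot see well enough in the lenses, or cannot handle them, gives way to one who can. The spectacle arm has no such step.

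Second, discomfort and low motivation are close to what the questionnaires measure. A subject who stops for either reason is likely to be a low scorer, and the visible text does not collect that score. The rule that all data are included cannot restore data never collected, and any exclusion is judged by people who can see the allocation.

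With about 15 subjects per arm, two or three missing low scores could shift the result, and they cannot be recovered later.

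**Working it through.** **Order of events in section 3.2.2**

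1. Step 13: eligibility is confirmed. Step 14: the subject is randomised. Spectacle subjects then go straight to step 22, the mask supply.
2. Steps 15 and 16, lens arm only: lenses are fitted and acuity is measured in them. Inclusion criterion 11 sets an acuity limit with the study lenses where relevant. In the visible schedule that part of the criterion cannot be tested before step 16. A failure there falls under the discontinue-and-replace rule of section 2.2.
3. Step 21, lens arm only: lenses are dispensed only when the investigator is satisfied with handling. A subject who never reaches that point falls under the replacement rule of section 2.1.1.

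Both exits come after allocation, exist in one arm only and depend on how the assigned treatment went.

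**Where an exit score might be collected.** Sections 2.1.1, 2.2, 3.1.2 and 3.4 contain no rule for one. Section 3.2.4 covers only subjects leaving with significant signs or symptoms and names no questionnaire. Section 3.1.1 records data from unscheduled visits but does not specify scores.

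**Rescheduling.** If lenses are dispensed at the initial visit, the target is day 14 and the window closes on day 20, leaving 20 − 14 = 6 days to return. A subject who returns is scored on a lens-wearing day, so this route does not by itself lose the score.

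**The plan's own figures.** Section 2.1 consents up to 35 subjects for 15 completers per group: 35 − 30 = 5, and 5/35 = 14.3%. No loss by arm is given. The target of 15 cannot be reproduced, because no error rate, power, effect size or SD is visible (section 1.5.1 is redacted).

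**Illustration of size.** If k of n lens subjects are lost, the completers' mean exceeds the mean for all n by

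bias = (k/n) × gap,

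where gap is the completers' mean minus the mean the lost subjects would have given. Assumed, not in the documents: n = 17 or 18 (about half of 35), k = 2 or 3, gap = 1 or 2 points on a 1-to-5 scale, and no loss in the spectacle arm.

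| Lost | Share | Gap 1 | Gap 2 |
|---|---|---|---|
| 2 of 18 | 0.111 | 0.11 | 0.22 |
| 2 of 17 | 0.118 | 0.12 | 0.24 |
| 3 of 18 | 0.167 | 0.17 | 0.33 |
| 3 of 17 | 0.176 | 0.18 | 0.35 |

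If the spectacle arm also loses subjects with the same gap, the net bias per point of gap is the difference in shares. With 3 of 18 lens subjects lost and 1, 2 or 3 of 17 spectacle subjects lost, it is 0.108, 0.049 or −0.010.

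**Effect on the test.** With an assumed SD of 1 point and 15 per arm, the standard error is √(2/15) = 0.365. By normal approximation, the two-sided error at a nominal 5% is Φ(b/0.365 − 1.96) + Φ(−b/0.365 − 1.96). This gives 0.062 for b = 0.12 and 0.160 for b = 0.35.

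**The case against.** The strongest reply is that the plan already limits the damage. Lens subjects arriving without lenses are asked back, non-attenders are pursued, all data are kept by default, and exclusions and numbers analysed must be reported. Parts of sections 1.5 and 3.2.3 are redacted, so a missing-data method or exit procedure may exist out of sight. The stated aim is exploratory. All of this stands, and it lowers the likely number of missing scores. It does not touch the replacement of randomised lens subjects, which is in unredacted text.

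A reader might also infer more than the documents support:

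- **That attending without lenses means no two-week score.** The rule is to reschedule. The score is lost only if the subject never returns; otherwise scoring moves to a lens-wearing day, a weaker form of selection.
- **That section 2.2 acts mainly on the lens arm.** Its wording covers both arms. Everyone had to be willing to be fitted with lenses, so disappointed spectacle subjects could lose motivation too. More loss among first-time lens wearers is plausible but not written.
- **That the bias is certain and its direction known.** No loss by arm and no score gap is given, and balanced losses would roughly cancel.
- **That all five spare subjects could be lens-arm losses, for example 5 of 20.** The 35 are counted at consent, before eligibility is confirmed, so the margin also has to cover screening failures who are never randomised.
- **That the five-point scale measures satisfaction with vision correction.** The visible scale is for mask usability (breathability, heat, tightness and similar items). The satisfaction scale is not visible.

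**Conclusion.** The concern holds as a risk: the two-week comparison may be biased towards lenses. The firm part is the lens-only replacement after randomisation for acuity or handling failure. The second part is the absence, in the visible text, of any score from subjects in either arm who are discontinued for discomfort or low motivation. The one-sided rescheduling sentence is a lesser matter.

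The size is unknown. The 0.11 to 0.35 points illustrate scale only. They rest on an assumed number randomised (with no allowance for screening failures), assumed losses in one arm only, an assumed gap of 1 to 2 points, and a five-point scale that the documents show only for mask usability. The error rates of about 6% to 16% also need the assumed SD of 1 point. The point justifies a change because the remedy is cheap and the missing scores cannot be obtained afterwards.

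**What to change.** Leave the stopping rules as they are and change data collection and analysis:

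1. In sections 2.1.1 and 2.2, state that a randomised subject stays in the analysis in the assigned group, and that replacement in the analysis applies only before randomisation.
2. Ask every randomised subject to complete the existing follow-up questionnaires at exit or at two weeks, in person or remotely, whether or not still using the assigned correction.
3. In section 3.2.3, have questionnaires completed at the attended visit in both arms, with wear status recorded. Reschedule only the on-eye lens measurements.
4. Report losses by arm and reason. Add a sensitivity analysis over a range of assumed scores for those missing, varied separately by arm. Automatic worst-score imputation is not advised: it would fall mostly on the lens arm and could build in the opposite bias. It would also give the worst mask score to someone who never used the lenses with a mask in daily life.

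The cost is short edits to three sections and one extra analysis. The downside is a few questionnaires from people not wearing the assigned correction, and a lens result that may be less favourable.
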